8.1 Adverse events

8.1.1 Definitions and reporting

An adverse event is defined as the appearance of (or worsening of any pre-existing) undesirable sign(s), symptom(s), or medical condition(s) that occur after patient's signed informed consent has been obtained.

Abnormal laboratory values or test results occurring after informed consent constitute adverse events only if they induce clinical signs or symptoms, are considered clinically significant, require therapy (e.g., hematologic abnormality that requires transfusion or hematological stem cell support), or require changes in study medication(s).

Any ongoing adverse events from the parent study will be captured as medical history in the roll-over database. Any AE that begins (or worsens) after signing of the informed consent for the roll-over and during the 30-day (or 28-day) or 84-day (12 week) safety follow up period defined in the parent protocol should be reported in both clinical databases.

Adverse event monitoring should be continued for at least 30 days for patients receiving the s.c. formulation and 84 days for those receiving the LAR formulation (or 5 half-lives), whichever is longer) following the last dose of study treatment. Adverse events (including lab abnormalities that constitute AEs) should be described using a diagnosis whenever possible, rather than individual underlying signs and symptoms. When a clear diagnosis cannot be identified, each sign or symptom should be reported as a separate Adverse Event.

Adverse events will be assessed according to the current version of Common Terminology Criteria for Adverse Events (CTCAE).

If CTCAE grading does not exist for an adverse event, the severity of mild, moderate, severe, and life-threatening, corresponding to Grades 1 - 4, will be used. CTCAE Grade 5 (death) will not be used in this study; rather, information about deaths will be collected through the EOT eCRF page.

The occurrence of adverse events should be sought by non-directive questioning of the patient (subject) during the screening process after signing informed consent and at each visit during the study. Adverse events also may be detected when they are volunteered by the patient (subject) during the screening process or between visits, or through physical examination, laboratory test, or other assessments. As far as possible, each adverse event should be evaluated to determine:

1. The severity grade (CTCAE Grade 1-4)
2. Its duration (start and end dates)

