8.1.2 Laboratory test abnormalities

8.1.2.1 Definitions and reporting

Laboratory abnormalities that constitute an Adverse event in their own right (are considered clinically significant, induce clinical signs or symptoms, require concomitant therapy or require changes in study treatment), should be recorded on the Adverse Events CRF. Whenever possible, a diagnosis, rather than a symptom should be provided (e.g. anemia instead of low hemoglobin). Laboratory abnormalities that meet the criteria for Adverse Events should be followed until they have returned to normal or an adequate explanation of the abnormality is found. When an abnormal laboratory or test result corresponds to a sign/symptom of an already reported adverse event, it is not necessary to separately record the lab/test result as an additional event.

Laboratory abnormalities, that do not meet the definition of an adverse event, should not be reported as adverse events. A Grade 3 or 4 event (severe) as per CTCAE does not automatically indicate a SAE unless it meets the definition of serious as defined below and/or as per investigator's discretion. A dose hold or medication for the lab abnormality may be required by the protocol in which case the lab abnormality would still, by definition, be an adverse event and must be reported as such.

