14.2 Appendix 2: Recommended hepatic safety management guidance

Patients with transaminase increase combined with TBIL increase may be indicative of potential DILI, and should be considered as clinically important events.

If any of the criteria below are observed at any routine examinations (standard of care),

- ALT or AST $> 3 \times$ ULN and Total Bilirubin $\geq 2 \times$ ULN.
- ALT or AST $> 5 \times$ ULN and $\leq 8 \times$ ULN.
- ALT or AST $> 8 \times$ ULN, patient should be discontinued.

The following should be performed immediately within **72 hours** of awareness of the abnormality (for further details refer to [Figure 14-1](#)):

- Perform liver-directed medical history and physical examination (i.e. assess occupational hazards, concomitant medications including OTC meds, inter-current illness, etc).
- Liver chemistry tests: ALT, AST, total bilirubin, (fractionate to direct/indirect bilirubin if total bilirubin is $> 2.0 \times$ ULN), Alb, PT (INR), ALP, and GGT.
- Perform hepatitis screen: anti-HAV, IgM (to confirm acute Hepatitis A), HbsAg, Anti-HBc, anti-HCV (if positive, PCR viral load should be assessed), Anti-HEV, ANA antibodies, anti-smooth muscle anti-bodies, CMV and EBV.
- Perform abdominal ultrasound (liver and biliary tree).

[figure not shown]
Liver chemistry tests (LFTs) should be monitored every **3-4 days** until resolution or return to baseline status.

Patients or subjects may need to be discontinued if the abnormal liver function criteria are met upon LFT retesting. Progress reports of the event should be maintained until resolution or stabilization (i.e. no further elevation after 2 consecutive assessments).

For ALT or AST $> 5 \times$ ULN and $\leq 8 \times$ ULN, the following must occur (in addition to the safety follow up procedures noted above).

- Study medication should be temporarily interrupted and liver chemistry tests monitored every **3-4 days** until resolution or return to baseline.
- If resolution (ALT and AST ≤ 5 ULN) or return to baseline does not occur after 2 weeks, the patient should be discontinued.
- If ALT or AST return to less than 5 x ULN study drug can be resumed and patient can continue study per protocol.
- If ALT or AST rises above 5 x ULN any time after study drug is resumed, then study drug should be discontinued immediately.

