If any of these criteria are met and deemed an adverse event by the investigator, the event must be recorded on the Adverse Event (e) CRF page; if the event is deemed serious by the investigator, then proceed with completing the SAE form. In addition, any significant findings from the physical examination should be recorded on the Adverse Event (e) CRF page.

[figure not shown]
Figure 14-1 Recommended LFT management guidance

14.3 Appendix 3: Recommended guidance for follow up in case of QT-related findings during routine ECG

If at any routine ECG a QTcF > 500 msec is observed, triplicate ECGs, each 2-3 minutes apart, need to be collected approximately 1 hour after the initial ECG. The mean QTcF from the triplicate ECGs will be determined and if the mean QTcF > 500 msec, study treatment should be interrupted until a cardiologist has re-evaluated the ECG. Patient reassessment should be performed as early as possible but within 7 days of the initial abnormal ECG by a cardiologist for cardiovascular risk factors and a decision regarding study continuation.

If mean QTcF > 480 msec / ≤ 500 msec is observed, the repeat ECG assessment must be performed as soon as practical but within 7 days of the initial abnormal ECG. In addition, the following steps need to be taken (for more details refer to [Figure 14-2](#) below):

- If a QTcF > 480 msec / ≤ 500 msec is confirmed and QTcF change from pretreatment exceeds 60 msec, cardiology consultation must be sought as soon as practical (within 7 days) for ECG re-evaluation and clinical assessment for cardiovascular risk factors and a decision regarding study continuation.
- If a QTcF > 480 msec / ≤ 500 msec is confirmed and QTcF change from pretreatment < 60 ms, more frequent ECG follow-up is advised.

Figure 14-2 Recommended guidance for ECG follow up

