Pregnancy tests will be listed overall and by indication and formulation.

4.2 *Patient disposition, demographics and other baseline characteristics*

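### Appendix 2 leaves AE recording of liver abnormalities to the investigator, while Section 8.1 makes those that force a hold or stop of drug AEs by definition, so liver events in the primary endpoint could be under-counted

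*Protocol*

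**What the plan says.** Protocol Section 8.1.1 treats an abnormal laboratory value as an AE on any of several grounds, one of which is that it requires a change in study medication. Section 8.1.2.1 repeats the test for laboratory abnormalities, which, if they "require concomitant therapy or require changes in study treatment), should be recorded on the Adverse Events CRF". It adds that where the protocol itself requires a dose hold, "the lab abnormality would still, by definition, be an adverse event and must be reported as such".

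Appendix 2 lists three liver criteria: ALT or AST above 3 × ULN with total bilirubin at least 2 × ULN; ALT or AST above 5 and up to 8 × ULN; and ALT or AST above 8 × ULN. For the second it instructs that "Study medication should be temporarily interrupted and liver chemistry tests monitored every" 3 to 4 days. For the third it says "ULN, patient should be discontinued". Its closing paragraph then sets the recording rule: "If any of these criteria are met and deemed an adverse event by the investigator, the event must be recorded" on the AE page.

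The primary endpoint is the frequency and severity of AEs and SAEs (protocol Table 3-1); SAP Section 7.1.1 adds AESIs. For laboratory data the SAP says only "Pregnancy tests will be listed overall and by indication and formulation" (Section 4.1), and protocol Section 10.5.3.3 marks other safety data as not applicable.

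**The concern.** Two current provisions give different recording rules for the same liver event. Under Section 8.1 the treatment consequence settles whether it is an AE. Under Appendix 2 a second condition, the investigator's opinion, stands between the event and the AE page. Protocol Section 7.2.2.1 sends sites to Appendix 2 when they find a liver abnormality, so that is the text they are likely to have open.

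A site could therefore interrupt or stop pasireotide for a transaminase rise, believe it had followed the protocol, and enter no AE. Section 2.6 names transient transaminase elevation among the expected effects of the drug, so the situation is foreseeable. The event would then be missing from the overall AE table, the liver AESI table, and the tables of AEs leading to discontinuation or requiring dose adjustment or interruption (SAP Sections 7.4.1 and 8.2). An omission can only lower these counts.

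**Working it through.** This is a comparison of texts; the plan has no figure to reproduce.

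**Step 1. Set the rules side by side.**

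| Liver finding | Treatment consequence in the readable text | AE under Sections 8.1.1 and 8.1.2.1? | AE entry under Appendix 2? |
|---|---|---|---|
| ALT/AST >5 to ≤8 × ULN | Interruption (Appendix 2); discontinuation if it lasts beyond 2 weeks (Appendix 2, Section 7.1.5.1) | Yes, by definition | If deemed an AE |
| ALT/AST >8 × ULN | Discontinuation (Appendix 2, Section 7.1.5.1) | Yes, treatment must change | If deemed an AE |
| ALT/AST >3 × ULN (not above 5) with bilirubin ≥2 × ULN, ALP <2 × ULN | No hold stated in Appendix 2; discontinuation in Section 7.1.5.1 | Yes, through Section 7.1.5.1 | If deemed an AE |
| Same, but ALP ≥2 × ULN | No mandatory hold or stop stated | Depends on the other tests, such as clinical significance | If deemed an AE |

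The conflict is direct in the first two rows, arises through the main body in the third, and is absent in the fourth. Figure 14-1 could not be read here. It might bear on the last two rows, but not on the first two, which rest on text.

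**Step 2. Look for a limit on the discretion.** The closing paragraph of Appendix 2 does not refer to Section 8.1. It sends significant physical-examination findings to the AE page without asking whether they are deemed AEs, so the extra condition applies to the laboratory criteria and not to the examination findings.

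**Step 3. Trace an omitted event through the SAP.** The tables in Section 7.4.1 are built from AE records. ALT and AST terms belong to the liver AESI category in Section 8.2. No analysis of liver test values is planned that could recover the event. Two other outputs could show traces: interruptions and reductions with reasons (Section 7.3), and the primary reason for ending treatment (Section 4.2.1). Neither feeds AE or AESI counts, and no reconciliation between them and the AE data is specified. Deviation D01 in Section 8.1 of the SAP covers a patient who met hepatic stopping criteria and was not withdrawn. It does not cover one who was withdrawn without an AE entry.

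**Step 4. Ask whether the size can be computed.** Let N be the number of liver events that are AEs under Section 8.1 and u the share not entered. The tables show N(1 − u), so the relative shortfall is [N − N(1 − u)] / N = u. The documents give neither N nor u, and u may be 0.

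**The case against.** The best reply is that the texts can be read together. Appendix 2 does not say that events are recorded only if deemed AEs, and an investigator should deem by the protocol's own definition. Section 7.2.2 refers to Section 8 for AE collection, while the appendix is titled as recommended management guidance. On that reading nothing is lost. The reading is available, and some sites will adopt it. It does not remove the discretionary wording from the place where sites are sent for liver findings. Nor does the guidance label help much: Section 6.2 refers to the same appendix for dose modification, and the Section 8.1.1 test is whether the abnormality requires a treatment change.

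A second reply is that data checks will catch omissions. Section 9.4 provides for discrepancy queries. However, Section 9.2 requires full verification only for consent, eligibility and SAE documentation, and leaves other checks to a monitoring plan outside these documents.

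A third objection stands. A reader might infer that every Appendix 2 criterion is already an AE under Section 8.1.2.1, so that the deeming phrase can simply be struck out. The documents do not support this. The fourth row of the table carries no stated mandatory hold or stop. Section 8.1.2.1 also excuses separate recording of a result that belongs to an AE already reported, and Section 8.1.1 takes AEs ongoing from the parent study as medical history. Blanket deletion would create new conflicts.

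**Conclusion.** The inconsistency is real, and the two passages must be reconciled. It allows liver AEs and AESIs to be missed in the primary endpoint, with any error towards fewer events. This assumes that at least some sites apply the Appendix 2 sentence as it stands.

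Two stronger conclusions are tempting and not supported. One is that a particular fraction of liver events is lost: as Step 4 shows, any percentage would only restate an assumed unrecorded share. Under-counting is possible, not shown. The other is that an unrecorded event disappears from the report. Reasons for dose change and for ending treatment are a partial backstop, although they leave the AE counts uncorrected.

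The study is descriptive and tests no hypothesis, so no error rate or power is affected. The point still merits action because it concerns the primary endpoint and can be dealt with cheaply.

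**What to change.** 1. At the next amendment, reconcile the closing sentence of Appendix 2 with Section 8.1. A liver abnormality that leads to a protocol-required interruption or discontinuation is recorded as an AE, unless it corresponds to an AE already reported, as Section 8.1.2.1 allows. Investigator judgement stays for seriousness and for the remaining abnormalities.
2. Until then, remind sites that Section 8 governs AE recording. A reminder cannot change the text: Section 12.1 requires a written amendment with the stated approvals.
3. Before database lock, run a programmed reconciliation. Query each dosing-record interruption or reduction, and each end-of-treatment record, that gives a laboratory or liver reason and has no matching AE. This uses data already collected and can recover past omissions, which the wording change cannot.

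The cost is a small amendment, one listing with its queries, and possibly slightly higher reported liver AE rates. No clinical threshold or dosing rule changes.

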14.4 Appendix 4: Recommended guidance for fasting blood glucose management

Hyperglycemia

Two clinical studies ([\[SOM230B2216\]](#) and [\[SOM230B2124\]](#)) have been conducted in healthy volunteers to further understand the mechanism of pasireotide-induced hyperglycemia and to evaluate the potential clinical utility of anti-diabetes agents in the management of pasireotide-induced hyperglycemia. Data from SOM230B2216 indicate that pasireotide decreases insulin, GLP-1 and GIP secretion, particularly in the postprandial period. Results from SOM230B2124 suggest that the incretin-based therapies (GLP-1 analogues and DPP-4 inhibitors) may have the best potential to manage the hyperglycemia associated with pasireotide. In phase II and III studies, some patients with Cushing's disease, acromegaly or neuroendocrine tumor required insulin to treat hyperglycemia.

Glucose monitoring

All patients need to be educated on the signs and symptoms of hyperglycemia. Patients must monitor their fasting blood glucose by fingerstick at home. It is recommended that a diary of the blood glucose values is used for appropriate management throughout the study. The collected data should be presented to the physician/diabetes specialist for evaluation. This data will not be collected by the sponsor.

Blood glucose monitoring

Close and frequent glucose monitoring is recommended during pasireotide treatment.

[figure not shown]
- If any fasting values above 100 mg/dL are observed, the guidelines in [Figure 14-3](#) are to be followed. These guidelines are based on the current recommendations from the 2012 ADA and EASD aiming at a glycemic treatment goal of FPG <130 mg/dL (<7.2 mmol/L) (Inzucchi, SE et al. DiabetesCare June 2012 vol. 35 no. 6 1364-1379). Appropriate actions, such as initiation of anti-hyperglycemic therapy (and referral to diabetes specialist), are to be taken by the investigator as outlined on [Figure 14-3](#).
- If fasting blood glucose values dictate initiation of anti-hyperglycemic treatment (i.e., confirmed >130 mg/dL by self-monitoring), a fasting plasma glucose sample can be collected prior to initiation of anti-hyperglycemic treatment.
- In case of dose increase, the glucose monitoring frequency should be increased following the recommendations described above at treatment initiation

FPG and HbA1c monitoring

- If FPG > 130 mg/dL or HbA1c \geq 6.5 %, intervention for hyperglycemia needs to be implemented
- If FPG > 160 mg/dL or HbA1c >7.5%, despite optimal anti-diabetic therapy, referral to a diabetologist is recommended.
- If grade 3 hyperglycemia (FPG >250 mg/dL; >13.9 mmol/L) at any point in the study, despite appropriate anti-diabetic medication, pasireotide dose should be reduced
- If consistently high glucose values [FPG \geq 240 mg/dL (13.3 mmol/L) or HbA1c \geq 10 %] despite appropriate management of diabetes including diet and/or exercise with or without

optimal anti-diabetic therapy and study drug dose reduction, patient must be discontinued from study treatment as outlined in [Section 7.1.5.1](#). After the last study dose was received, patients have to monitor their fasting blood glucose for 1 month

Figure 14-3 Recommended guidance for fasting self-monitoring blood glucose management

14.5 Appendix 5: Dose modification information for acromegaly or carcinoid patients receiving pasireotide LAR (from protocol CSOM230C2110, CSOM230C2305, CSOM230C2402 and CSOM230C2413)

At any time during the roll-over, the pasireotide LAR dose may be increased up to a maximum dose of 60 mg per injection if biochemical control is not achieved, i.e. when their GH level \geq 2.5 μ g/L and/or IGF-1 > ULN (age and sex related). Also the pasireotide LAR dose may be reduced if a patient is experiencing a drug related toxicity. The dose should be adjusted in 20 mg steps, e.g. the pasireotide LAR dose can be adjusted from 60 mg to 40 mg or from 40 mg to 20 mg. The decision to change the dose is to be made by the investigator or designee, and the dose change must be recorded in the Dosage Administration Record CRF. Patients should return to the previous dose once the tolerability issue resolves.

Study C2413 specific: The minimum dose to be administered is 10 mg for patients with IGF-1 levels falling below the lower limit of normal and have controlled mean GH levels. The IGF-1 values are required to be confirmed to be below LLN on two consecutive assessments. If biochemical control is maintained, the patient can continue on the lower dose for the remainder of the trial. If biochemical control is lost, the dose should be increased. The 10 mg dose should be obtained from the 20 mg vial.

Table 14-1 Dose modification for AEs, excluding LFT increase, QT prolongation and hyperglycemia

Adverse event	Action
CTCAE grade \leq 2	No drug adjustments
CTCAE grade \geq 3 and assessed as study drug related	
Reduce pasireotide to the next lower dose level.
 
 If the AE improves to grade \leq 2 before the next administration, increase dose back to the prior dose. If the dose is increased and the AE recurs at a grade \geq 3, the dose should be reduced again. The patient should stay on this lower dose and no further dose titrations are allowed. If the AE does not improve to grade \leq 2, the dose is to be reduced further. If the AE does not improve to grade \leq 2 on the minimum study dose, the treatment should be stopped.

For the management of LFT increase, QT prolongation, and hyperglycemia refer to specific instructions provided in [Appendix 2](#), [Appendix 3](#) and [Appendix 4](#).

Table 14-2 Dose adjustments for pasireotide LAR for patients from SOM230C2110

Dose (mg)	Volume to be injected
20 mg	2 x 10 mg vial + 2 mL vehicle: whole volume to be injected or 1 x 20 mg vial + 2 mL vehicle: whole volume to be injected
40 mg	1 x 40 mg vial + 2 mL vehicle: whole volume to be injected
60mg	2 x 10 mg vial + 1 x 40 mg vial + 2 mL vehicle; whole volume to be injected or 1 x 20 mg vial + 1 x 40 mg vial + 2 mL vehicle; whole volume to be injected

Table 14-3 Dose adjustments for pasireotide LAR for patients from SOM230C2305

Dose (mg)	Volume to be injected
20 mg	1 x 20mg vial + 2 mL vehicle, whole volume to be injected
40 mg	1 x 40mg vial + 2 mL vehicle, whole volume to be injected
60 mg	1 x 20mg + 1 x 40mg vial + 2 mL vehicle, whole volume to be injected

Table 14-4 Dose adjustments for pasireotide LAR for patients from SOM230C2402

Dose (mg)	Volume to be injected
40 mg	1 x 20 mg vial + 1 x 20 mg vial + 2 mL vehicle, whole volume to be injected
60 mg	1 x 20 mg + 1 x 40 mg vial + 2 mL vehicle, whole volume to be injected

14.6 Appendix 6: Dose modification information for Cushing's patients receiving pasireotide LAR (from protocol SOM230G2304)

Dose up-titration

Patients will receive the same dose of pasireotide LAR as the last dose in the parent study. The maximum dose to be administered is 40 mg. Dose can be increased from 10 to 30 mg and from 30 to 40 mg. During the roll-over study, the timing of the dose adjustments will be based on mUFC values, at the investigators discretion but must include a duration of at least 3 months on a current dose prior to up-titration and no tolerability issues are present. Patients receiving the 40 mg dose after Month 12 without tolerability issues that require a dose reduction will remain at this dose regardless of mUFC status ($\leq 1x$ ULN or $> 1 x$ ULN).

Dose down-titration

Patients with tolerability issues can have their dose decreased as deemed necessary by the investigator (see [Table 14-5](#)). The dose can be increased again after the tolerability issue resolves. Patients unable to tolerate a minimum dose of 5 mg will be discontinued.

These changes must be recorded on the Dosage Administration Record CRF.

Table 14-5 Dose modification for AEs, excluding LFT increase, QT prolongation and hyperglycemia

Adverse event	Action
AE CTC grade ≤ 2	No drug adjustments
AE CTC grade ≥ 3 and assessed as study drug related	Reduce pasireotide LAR i.m. dose from: 40mg to 30 mg 30 mg to 10 mg 10 mg to 5mg 5mg - discontinue If AE improves to grade ≤ 2 before the next administration, increase dose to that prior to the dose reduction unless investigator opinion is to remain on current dose. If the dose is increased and the AE recurs at CTC grade ≥ 3 , the dose should be reduced again and the patient should stay on this lower dose and no further dose titrations are allowed. During the first 7 months of treatment, only 1 blinded dose decrease is allowed. If the AE persists at grade ≥ 3 after reduction, the patient is to be discontinued. After the first 7 months, If AE does not improve to grade ≤ 2 the dose is to be reduced further until the 5 mg dose is reached. If the AE does not improve to grade ≤ 2 on the minimum dose (5 mg) the patient will be withdrawn.

For the management of LFT increase, QT prolongation, and hyperglycemia refer to specific instructions provided in [Appendix 2](#), [Appendix 3](#) and [Appendix 4](#).

14.7 Appendix 7: Dose modification information for dumping syndrome patients receiving pasireotide s.c or LAR (from protocol SOM230X2203)

During the roll-over, dose increase will be allowed up to 60 mg (30, 40 and 60 mg) in the event that control is lost (glucose levels < 60 mg/dL at 90, 120, 150 **or** 180 min during the OGTT or presence of symptoms). The up- titration must be in increments of 10 mg with the exception of patients receiving 40 mg when an increment of 20 mg (from 40 mg to 60 mg) is allowed.

In case a dose reduction is needed due to toxicity ([Table 14-8](#)), the dose can be reduced to the immediate lower dose level ([Table 14-7](#)) **and can be kept at this level if necessary. The lowest dose level allowed is 10 mg.** In case a dose reduction is needed due to toxicity at 10mg, the patient can have a dose interruption up to 28 days from the intended day of the scheduled dose or can be discontinued and followed up for toxicity as defined in [Table 14-6](#). If a patient requires a dose interruption of more than 28 days due to toxicity, then the patient must be discontinued from the study and followed up for toxicity [Table 14-6](#). When treatment is interrupted or permanently discontinued due to an AE or abnormal laboratory value the patient must be followed at least once a week for 4 weeks, and subsequently in 4-week intervals, until resolution or stabilization of the event, whichever occurs first.

Patients will be followed for adverse events and serious adverse events for 56 days following the last dose of pasireotide LAR treatment and for 28 days in case of discontinuation during pasireotide s.c. treatment.

[Table 14-6](#) outlines the follow-up required for toxicities of specific types and CTCAE grades-

Table 14-6 Follow up evaluation (after treatment interruption)

Toxicity	Follow-up evaluation (after treatment interruption)
Hematology	If \geq CTCAE grade 3 neutropenia or \geq CTCAE grade 3 thrombocytopenia has been demonstrated, these parameters must be assessed at least twice a week until resolution to \leq CTCAE grade 1 and then at least weekly until stabilization.
Renal	If serum creatinine $\geq 2 \times$ ULN has been demonstrated, this parameter must be assessed at least twice a week until resolution to \leq CTCAE grade 1 or baseline to and then at least weekly until stabilization.
Hepatic	For details on hepatic safety management, please refer to Appendix 2: Hepatic Safety Management
Pancreatic	If amylase and/or lipase \geq CTCAE grade 3 has been demonstrated, these parameters must be assessed once at 2-4 days and once again at 7 days (± 1 day) and be repeated twice a week until resolution to \leq CTCAE grade 2 and then at least weekly until stabilization. A CT scan or other imaging study to assess the pancreas, liver and gallbladder must be performed within 1 week of the first occurrence of any \geq CTCAE grade 3 of amylase and/or lipase. In patients with serum triglycerides ≥ 500 mg/dL, urine amylase needs to be tested.
Endocrine/metabolic	For details on hyperglycemia management, please refer to Appendix 4: 'Fasting blood glucose management' .
Cardiac	For details on the follow-up and treatment of QT prolongation, please refer to Appendix 3 'Recommended follow up in case of QT-related findings during routine ECG'
Non-laboratory	Patients who experience non-laboratory AEs must be evaluated at least once a week following demonstration of the toxicity until resolution of the toxicity until stabilization of the toxicity, or until study completion.

Table 14-7 Dose reduction steps for pasireotide LAR monthly dosing q28d

Dose reduction*			
	Dose level - 0	Dose level - 1	Study Phase
Pasireotide LAR	60 mg q28d	40 mg q28d	Extension phase
Pasireotide LAR	40 mg q28d	30 mg q28d	Extension phase
Pasireotide LAR	30 mg q28d	20 mg q28d	Extension phase
Pasireotide LAR	20 mg q28d	10 mg q28d ***	LAR or Extension phases

*Dose reduction should be based on the worst toxicity demonstrated at the last dose.
*** The lowest dose allowed 10 mg.

Table 14-8 Dose modification for AEs, excluding LFT increase, QT prolongation and hyperglycemia

Adverse event	Action
CTCAE grade \leq 2	No drug adjustments
CTCAE grade \geq 3 and assessed as study drug related	
Reduce pasireotide to the next lower dose level.
 
• If the AE improves to grade \leq 2 before the next administration, increase dose back to the prior dose.• If the dose is increased and the AE recurs at a grade \geq 3, the dose should be reduced again. The patient should stay on this lower dose and no further dose titrations are allowed.• If the AE does not improve to grade \leq 2, the dose is to be reduced further. If the AE does not improve to grade \leq 2 on the minimum study dose, the treatment should be stopped.

For the management of LFT increase, QT prolongation, and hyperglycemia refer to specific instructions provided in [Appendix 2](#), [Appendix 3](#) and [Appendix 4](#).

14.8 Appendix 8: Dose modification information for patients with metastatic melanoma or metastatic Merkel cell carcinoma receiving pasireotide s.c (from protocol SOM230X2404)

Patients will continue receiving the dose of pasireotide LAR q28 d at the same dose received during the follow-up period (20, 40, 60 or 80 mg).

In case a dose reduction is needed due to toxicity, the dose can be reduced to the immediate lower dose level (from 80 mg q 28 d to 60 mg q 28 d, from 60 mg q 28 d to 40 mg q 28 d, and from 40 mg q 28 d to 20 mg q 28 d) and can be kept at this level if necessary for the duration of the study or until disease progression or death. However, the dose will not be re-escalated once reduced. In case patients receiving 20 mg q 28 d need to reduce the dose further, they should be discontinued from the study. If a patient requires a dose interruption of > 7 consecutive days from the intended day of the scheduled dose, then the patient must be discontinued from the study and only follow up for toxicity defined in (reference **table below**).

When treatment is interrupted or permanently discontinued due to an AE or abnormal laboratory value the patient must be followed at least once a week for 4 weeks, and subsequently in 4-week intervals, until resolution or stabilization of the event, whichever occurs first.

Patients who experience non-laboratory AEs should be evaluated at least once a week following demonstration of the toxicity until a resolution of the toxicity or study treatment completion occurs.

Treatment interruption and treatment discontinuation

Patients experiencing unacceptable toxicity (AE grade 3 or higher) that the investigator considers directly attributable to pasireotide should have their dose reduced or should be withdrawn from the study. (reference **table below**) should be regarded as a guideline for the treatment of patients experiencing Adverse Events which are judged to be drug related. Any deviation from these guidelines should be discussed and approved by the sponsor.

Adverse events are described as mild (Grade 1), moderate (Grade 2), severe (Grade 3) or life-threatening (Grade 4). Guidelines for treatment of patients experiencing adverse events are indicated below (reference **table below**).

Table 14-9 Dose modification for AEs, excluding LFT increase, QT prolongation and hyperglycemia for patients from protocol SOM230X2402

Patients	Adverse event	Action
All	AE grade \leq 2 (mild to moderate)	No drug adjustments
	AE grade \geq 3 (severe to life-threatening) and judged as drug related**	
Reduce dose by 20 mg q 28 d to the next dose level as described above in this appendix (Appendix 8).
 
Once the dose is reduced, the patient will stay on the lowered dose for the entire duration of the roll-over
 
If AE recurs at grade \geq 3, reduce dose by 20 mg q 28 d again and remain at lower dose. If AE does not improve to grade \leq 2 the dose is to be reduced further (following the guidance as described above in this appendix (Appendix 8)). If the AE does not improve to grade \leq 2 on the minimum dose (20 mg q 28 d), patient is to discontinue treatment and followed for safety.

For the management of LFT increase, QT prolongation, and hyperglycemia refer to specific instructions provided in [Appendix 2](#), [Appendix 3](#) and [Appendix 4](#). For management of diarrhea, please refer to (reference below section)

